7.2 Participant Discontinuation/Withdrawal from the Study

A participant must be withdrawn in the event of any of the following:

- A participant may withdraw from the study at any time, at his/her own request or may be withdrawn at any time at the discretion of the Investigator for safety, behavioral, compliance, or administrative reasons.

Section 1.3 (Schedule of Activities) specifies the data to collect at study discontinuation and follow-up, and any additional evaluations that need to be completed.

In case of withdrawal from treatment, the day of End-of-Treatment will correspond to the day of withdrawal (or within 7 days). The assessments scheduled for this visit should be performed, if possible, with focus on the most relevant assessments. In case participant gets enrolled into new study or any new therapy post withdrawal from study, the Safety Follow-up Visit should be scheduled prior to start of the new treatment irrespective of the 28-day safety follow-up period. In either case, the appropriate eCRFs for the End-of-Treatment Visit must be completed. In case of withdrawal, participants will be asked to continue safety and survival follow-up, which includes the collection of data on survival and subsequent anticancer therapy. After completion of the Follow-up period or after the End-of-Treatment Visit, whichever is applicable, the appropriate eCRF section for Study Termination must be completed.

7.3 Lost to Follow-up

A participant will be considered lost to follow-up if he or she repeatedly fails to return for scheduled visits and is unable to be contacted by the study site.

The following actions must be taken if a participant fails to return to the clinic for a required study visit:

- The site must attempt to contact the participant and reschedule the missed visit as soon as possible, counsel the participant on the importance of maintaining the assigned visit schedule and ascertain if the participant wants to or should continue in the study.
- Before a participant is deemed “lost to follow-up”, the Investigator or designee must make every effort to regain contact with the participant: 1) where possible, make 3 telephone calls; 2) if necessary, send a certified letter (or an equivalent local method) to the participant’s last known mailing address, and 3) if a participant has given the appropriate consent, contact the participant’s general practitioner for information. These contact attempts should be documented in the participant’s medical record.
- Should the participant continue to be unreachable, he/she will be considered to have withdrawn from the study.

8 Study Assessments and Procedures

- Study assessments and procedures and their timing are summarized in Section 1.3 (Schedule of Activities).
- No protocol waivers or exemptions are allowed.
- Immediate safety concerns should be discussed with the Sponsor immediately upon occurrence or awareness to determine if the participant should continue or discontinue study intervention.
- Adherence to the study design requirements, including those specified in Section 1.3 (Schedule of Activities), is essential and required for study conduct.
- All Screening evaluations must be completed and reviewed to confirm that potential participants meet all eligibility criteria. The Investigator will maintain a screening log to record details of all participants screened, to confirm eligibility, and if applicable, record reasons for screening failure.
- Prior to performing any study assessments that are not part of the participant’s routine medical care, the Investigator will obtain written informed consent as specified in Appendix 2 (Study Governance).
- Procedures conducted as part of the participant’s routine medical care (e.g., blood count) and obtained before signing of the ICF may be used for screening or baseline purposes provided the procedures met the protocol-specified criteria and were performed within the time frame defined in Section 1.3 (Schedule of Activities).

8.1 Efficacy Assessments and Procedures

Contrast-enhanced computed tomography (CT) of chest/abdomen and pelvis covering the area from the superior extent of the thoracic inlet to the symphysis pubis is the first choice of imaging modality. The CT of the pelvis may be omitted if it is not part of the standard of care and CT of the abdomen includes the entirety of the liver and all other known sites of disease. If a participant cannot receive iodinated contrast, or if regional radiation regulations prevent full CT scan, magnetic resonance imaging (MRI) of the same area, using gadolinium enhancement (according to local protocol) is permitted in conjunction with unenhanced CT of the chest from the thoracic inlet to the inferior costophrenic recess. The same modality, and preferably the same scanner, should be used per participant throughout the study.

A brain CT/MRI scan should be performed at Baseline, and subsequently if clinically indicated by development of new specific symptoms. In this study, we modify RECIST 1.1 so that skin metastasis cannot be used as target lesions using measurements by caliper but may be selected if they fulfill RECIST 1.1 requirements for target lesions using CT/MRI scan (refer to RECIST 1.1 criteria).

A central imaging laboratory will be used to read and interpret all CT/MRI data; however, treatment decisions will be made by the treating Investigator. Response will be evaluated according to RECIST 1.1 and immune-related RECIST (irRECIST) 1.1 by IRC blinded for treatment CCI

Baseline scans are taken within 28 days, and preferably within 14 days, prior to randomization. All the scans performed at Baseline need to be repeated at subsequent visits for tumor assessment. In general, lesions detected at Baseline need to be followed using the same imaging methodology and preferably the same imaging equipment at subsequent tumor evaluation visits.

All during treatment scans are to be repeated using the same method at the subsequent assessment time points.

Participants will be evaluated every 6 weeks with radiographic imaging to assess response to treatment within 18 months of the participant's first dose, then every 12 weeks as scheduled in Section 1.3.

In the case of PD with discontinuation of treatment, any subsequent local tumor assessments (including scans under first subsequent treatment for OR as assessed by Investigator) should be documented in the eCRF. Confirmation after at least 4 weeks following first assessment is recommended for PD if the participant is not discontinued earlier. Any subsequent anticancer therapies and the date of any response and subsequent progression should be captured in the eCRF.

Participants who start 2L treatment should be monitored for response to that treatment as described in Section 4.1. Radiologic scans performed per local clinical practice used for monitoring response should be uploaded to the imaging repository.

8.2 Safety Assessments and Procedures

The safety profile of the study intervention will be assessed through the recording, reporting and analysis of baseline medical conditions, AEs, physical examination findings, including vital signs, ECOG PS, and laboratory tests.

Comprehensive assessment of any potential toxicity experienced by each participant will be conducted starting when the participants give the prescreening informed consent and throughout the study. The Investigator will report any AEs, whether observed by the Investigator or reported by the participant; the reporting period is specified in Section 8.3.1.

The AE reporting period for safety surveillance begins when the participant is initially included in the study (date of first signature of prescreening informed consent) and continues until last Safety Follow-up Visit or before start of any anticancer therapy, whichever comes first.

The safety assessments will be performed according to Section 1.3 (Schedule of Activities). Evaluations of the study data will be conducted by an IDMC to ensure safety and the validity and scientific merit of the study.

8.2.1 Clinical Safety Laboratory Assessments

- Blood and urine samples will be collected for the clinical laboratory tests listed in [Appendix 7](#), at the time points listed in Section 1.3 (Schedule of Activities). All samples should be clearly identified.
- Additional tests may be performed at any time during the study, as determined necessary by the Investigator or required by local regulations.
- The tests will be performed by the local laboratory.
- The Sponsor must receive a list of the local laboratory normal ranges before shipment of study intervention(s). Any changes to the ranges during the study must be forwarded to the Contract Research Organization (CRO) and the Sponsor.
- The Investigator must review each laboratory report, document their review, and record any clinically relevant changes occurring during the study in the AE section of the eCRF. The laboratory reports must be filed with the source documents.

If a participant has a clinically significant abnormal laboratory test value that is not present at Baseline, the test should be closely monitored until the test value has returned to the normal range or the Investigator has determined that the abnormality is chronic or stable.

The report of the results must be retained as a part of the participant's medical record or source documents.

Abnormal laboratory findings and other abnormal investigational findings (for example, on an ECG trace) should not be reported as AEs unless they are associated with clinical signs and symptoms, lead to treatment discontinuation, or are considered otherwise medically important by the Investigator. If a laboratory abnormality fulfills these criteria, the identified medical condition

(for example, anemia, increased ALT) must be reported as the AE rather than the abnormal value itself.

See Section 1.3 for the Schedule of Activities.

For female participants of childbearing potential, urine or serum beta-human chorionic gonadotropin (β -hCG) test will be performed according to Section 1.3 (Schedule of Activities). Results of the most recent pregnancy test should be available prior to the next dosing of study intervention. Participants who are not WOCBP (as defined in Section 5.1) are exempted from pregnancy testing, but reason must be documented.

8.2.2 Vital Signs, Physical Examinations, and Other Assessments

Vital signs, physical examinations, and ECOG PS will be conducted at Screening and at subsequent visits as indicated in Section 1.3 (Schedule of Activities). These should be documented in the eCRF.

Vital signs will be measured in a semi-supine position after 5 minutes rest and will include temperature, systolic and diastolic blood pressure, and pulse.

Blood pressure and pulse measurements will be assessed with a completely automated device. Manual techniques will be used only if an automated device is not available.

- A complete physical examination will include, at a minimum, assessments of the Cardiovascular, Respiratory, Gastrointestinal, Skin, and Neurologic systems. Height (at Screening) and weight will also be measured and recorded.
- A brief physical examination will include, at a minimum, assessments of pre-existing symptoms of underlying conditions and/or signs of infection and should be investigated as clinically indicated. Skin assessments should be performed as per Section 1.3 (Schedule of Activities) and as clinically indicated.
- Investigators should pay special attention to clinical signs related to previous serious illnesses.
- Abnormal findings are to be reassessed at subsequent visits.

A single 12-lead ECG will be obtained as outlined in Section 1.3 (Schedule of Activities) using an ECG machine that automatically calculates the heart rate and measures PR, QRS, QT, and QTc intervals.

8.3 Adverse Events and Serious Adverse Events

The definitions of an Adverse Event (AE) and a Serious Adverse Event (SAE) are in [Appendix 6](#).

8.3.1 Time Period and Frequency for Collecting Adverse Event and Serious Adverse Event Information

The AE reporting period for safety surveillance begins when the participant is initially included in the study (date of first signature of prescreening informed consent) and continues until the study's 28-day Safety Follow-up Visit, defined as 28 days (± 5 days) after the last study intervention administration. After the End-of-Treatment Visit, related AEs should be documented until the last Safety Follow-up Visit, defined as 12 weeks (± 2 weeks) after the last study intervention. Ongoing events at the 12-week Safety Follow-up Visit should continue to be monitored and documented until resolution or resolution with sequelae.

Any SAE assessed as related to study intervention must be recorded and reported, as indicated in [Appendix 6](#), whenever it occurs, irrespective of the time elapsed since the last administration of study intervention.

The method of recording, evaluating, and assessing causality of AEs (including SAEs) and the procedures for completing and transmitting SAE reports are in [Appendix 6](#).

8.3.2 Method of Detecting Adverse Events and Serious Adverse Events

At each study visit, the participant will be queried on changes in his or her condition. During the reporting period, any unfavorable changes in the participant's condition will be recorded as AEs, regardless if reported by the participant or observed by the Investigator.

Complete, accurate and consistent data on all AEs experienced for the duration of the reporting period (defined below) will be reported on an ongoing basis in the appropriate section of the eCRF. All SAEs must be additionally documented and reported using the appropriate Report Form as specified in [Appendix 6](#).

8.3.3 Follow-up of Adverse Events and Serious Adverse Events

AEs are recorded and assessed continuously throughout the study, as specified in Section 8.3.1 (Time Period and Frequency for Collecting Adverse Event and Serious Adverse Event Information) and are assessed for their outcome at the End-of-Treatment Visit. All SAEs ongoing at the End-of-Treatment Visit must be monitored and followed-up by the Investigator until stabilization or until the outcome is known, unless the participant is documented as "lost to follow-up". Reasonable attempts to obtain this information must be made and documented. It is also the responsibility of the Investigator to ensure that any necessary additional therapeutic measures and follow-up procedures are performed. Further information on follow-up procedures is given in [Appendix 6](#) (Adverse Events: Definitions and Procedures for Recording, Evaluating, Follow-up, and Reporting).

See Section 8.3.1 for the time periods for the collection of AEs and SAEs.

Monitoring of Specific Adverse Events

If monitoring is warranted for certain ADRs for safety issues, the treating physician or Investigator is requested to follow the participant during the post-treatment long-term follow-up phase until the end of study period or the participant is “lost to follow-up” and report the management and outcome of AEs to the Sponsor. See Section 6.9 (as applicable).

8.3.4 Regulatory Reporting Requirements for Serious Adverse Events

The Sponsor will send appropriate safety notifications to Health Authorities in accordance with applicable laws and regulations.

The Investigator must report SAEs (particularly deaths) in accordance with applicable site-specific requirements to the IRB that approved the study.

In accordance with international council for harmonisation and good clinical practice (ICH GCP) and the Japanese ministerial ordinance on GCP, the Sponsor/designee will immediately inform all the study Investigators and Heads of the study sites of findings that could adversely affect the safety of participants, impact the conduct of the study or alter the IRB’s approval/favorable opinion to continue the study. In line with respective applicable regulations, the Sponsor/designee will immediately inform all the study Investigators and the Heads of the study sites of AEs that are both serious and unexpected and considered to be related to the administered product (“suspected unexpected serious adverse reactions” or SUSARs). In addition, per applicable regulations, the Sponsor/designee will inform the study Investigators and the Heads of the study sites of all SAEs which were reported to the health authorities. In accordance with the Japanese regulatory requirements concerning safety reporting, the Investigator should place copies of the Safety Reports in the Investigator Site File. The Head of the study site should also maintain copies of safety reports appropriately.

When specifically required by regulations and guidelines, the Sponsor/designee will provide appropriate Safety Reports directly to the concerned lead IRB and will maintain records of these notifications. When direct reporting is not clearly defined by national or site-specific regulations, the Investigator will be responsible for promptly notifying the concerned Independent Ethics Committee (IEC)/IRB of any Safety Reports provided by the Sponsor/designee and of filing copies of all related correspondence in the Investigator Site File.

For studies covered by the European Directive 2001/20/EC, the Sponsor’s responsibilities regarding the reporting of SAEs/SUSARs/Safety Issues will be carried out in accordance with that Directive and with the related Detailed Guidance documents.

8.3.5 Pregnancy

Only pregnancies the Investigator considers to be related to the study intervention (e.g, resulting from a drug interaction with a contraceptive method) are AEs. However, all pregnancies with an estimated conception date during the period defined in Section 8.3.1 (Time Period and Frequency for Collecting Adverse Event and Serious Adverse Event Information) must be recorded in the AE page/section of the eCRF for both pregnancies in female participants and pregnancies in female partners of male participants. The Investigator must notify the Sponsor/designee in an expedited manner of any pregnancy using the Pregnancy Report Form, which must be transmitted by the same process specified for SAE reporting in [Appendix 6](#), section on Reporting Serious Adverse Events.

Investigators must actively follow-up, document and report on the outcome of all these pregnancies, even if the participants are withdrawn from the study.

The Investigator must notify the Sponsor/designee of these outcomes using the Pregnancy Report Form. If an abnormal outcome occurs, the SAE Report Form will be used if the participant sustains an event and the Parent-Child/Fetus Adverse Event Report Form if the child/fetus sustains an event. Any abnormal outcome (e.g., spontaneous abortion, fetal death, stillbirth, congenital anomalies, ectopic pregnancy) must be reported in an expedited manner, as specified in Section 8.3.1, while normal outcomes must be reported within 45 days after delivery.

A pregnant participant is not allowed to receive study intervention. The Sponsor/designee must be notified without delay if a participant becomes pregnant or impregnates while on study. The pregnancy must be followed as indicated above.

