AE = adverse event; β-hCG = beta-human chorionic gonadotropin; CR = complete response; CRF = case report form; CRT = chemoradiotherapy; CT = computed tomography; D = Day; ECG = electrocardiogram; ECOG PS = Eastern Cooperative Oncology Group Performance Status; EoT = End-of-Treatment; HBV = hepatitis B virus; HCV = hepatitis C virus; ICF = Informed consent form; MRI = magnetic resonance imaging; PD = progressive disease; PE = physical examination; PR = partial response; RT = radiation therapy; T₄ = free thyroxine; TSH = thyroid-stimulating hormone; V = visit; W = Week; WOCBP = woman of childbearing potential.

Table 3 Safety and Long-term Follow-up – M7824 and Pembrolizumab Arms

M7824 and Pembrolizumab Assessment	Safety Follow-up Visit		Long-term Follow-up		Notes
	28 Days (± 5 days) after Last Treatment	12 Weeks (± 2 weeks) after Last Treatment	Every 6 weeks (± 1 week)	Every 12 weeks (± 1 week)	
Documentation concomitant therapy	X	X		X	
Documentation of AEs	X	X		X ^{a,b}	See Appendix 6 for safety recording and reporting and see Section 7.1 in case of discontinuation from the study intervention a: The 12-week Safety Follow-up and Long-term Follow-up may be conducted via telephone calls b: See Section 8.3.1 for definition of the AE Reporting Period and Section 8.3.3 for Follow-up of AEs/SAEs
Physical examination	X				Focused PEs to be performed as per local standard practice.
Skin assessment	X				
Vital signs	X				Including weight
ECOG PS	X				
12-lead ECG	X				
Hematology and hemostaseology	X				Details on blood tests under this category are listed in Table 16 . Samples must also be drawn and results for core chemistry, hematology, and pregnancy test reviewed prior to dose administration
Full serum chemistry Panel A	X				See Table 16 for individual tests in each laboratory panel.
Urinalysis	X				
β-hCG pregnancy test	X				β-hCG should be determined from urine or serum.
Free T ₄ and TSH	X				
Subsequent anticancer therapy (any line)	X	X	X		
Survival follow-up				X	

M7824 and Pembrolizumab Assessment	Safety Follow-up Visit		Long-term Follow-up		Notes
	28 Days (± 5 days) after Last Treatment	12 Weeks (± 2 weeks) after Last Treatment	Every 6 weeks (± 1 week)	Every 12 weeks (± 1 week)	

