5. Contraceptive use by males or females will be consistent with local regulations on contraception methods for those participating in clinical studies.

Male participants are eligible to participate if they agree to the following during the intervention period and for at least 4 months after the last dose of study intervention:

- Refrain from donating sperm

PLUS, either:

- Abstain from intercourse with a female

OR

- Use a male condom

When having sexual intercourse with a woman of childbearing potential (WOCBP), who is not currently pregnant, and advise her to use a highly effective contraceptive method with a failure rate of $< 1\%$ per year, as described in [Appendix 3](#) since a condom may break or leak

Female participants:

Are not pregnant or breastfeeding, and at least one of the following conditions applies:

- Not a WOCBP

OR

• If a WOCBP, use a highly effective contraceptive method (i.e., with a failure rate of < 1% per year), preferably with low user dependency, as described in [Appendix 3](#) for the following time periods:

- Before the first dose of the study intervention(s), if using hormonal contraception:
 - Has completed at least one 4-week cycle of an oral contraception pill and either had or has begun her menses

OR

- Has used a depot contraceptive or extended-cycle oral contraceptive for least 28 days and has a documented negative pregnancy test using a highly sensitive assay.
- During the intervention period.
- After the study intervention period (i.e, after the last dose of study intervention is administered) for at least 4 months after the last dose of study intervention.
- Have a negative pregnancy test, as required by local regulations, on W1D1 before the first dose of study intervention.

Additional requirements for pregnancy testing during and after study intervention are in Schedule of Activities.

The Investigator reviews the medical history, menstrual history, and recent sexual activity to decrease the risk for inclusion of a female with an early undetected pregnancy.

Informed Consent

6. Capable of giving signed informed consent, as indicated in [Appendix 2](#) (Study Governance), which includes compliance with the requirements and restrictions listed in the informed consent form (ICF) and this protocol.

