6.8.1.2 Additional Potential Risks

Alterations in Wound Healing or Repair of Tissue Damage

Due to the involvement of TGF β in tissue and skin repair, alterations in wound healing or repair of tissue damage is considered an important potential risk. No relevant event is reported in the ongoing M7824 clinical studies. Monitoring of any surgical wounds while on study is recommended. In general, a 2-week delay from treatment is recommend following minor surgery and 4 week delay for major surgery, but cases should be discussed with the Medical Monitor.

Embryo-fetal Toxicities

Embryo-fetal toxicities are a known risk of the PD-1/PD-L1 targeting class. Animal models link the PD-1/PD-L1 signaling pathway with maintenance of pregnancy through induction of maternal immune tolerance to fetal tissue (Guleria, 2005; Leber, 2010; Wafula, 2009; Zenclussen, 2013).

Embryo-fetal and reproductive toxicities have also been investigated in animal models for a humanized monoclonal antibody targeting TGF β 1. At doses as high as 30 mg/kg, no maternal reproductive toxicity or embryo-fetal lethality were observed in rabbits (Hilbish, 2016). To mitigate these potential risks, pregnant participants are excluded from the study, and all participants of childbearing/conceiving potential must use highly effective contraception.

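### Protocol 8.3.5 ties eCRF recording of pregnancies to a conception window shorter than the 4-month contraception period in 5.1, and its recording, notification and follow-up rules do not agree

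*Protocol*

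**What the plan says.** **Recording.** Protocol 8.3.5 treats a pregnancy as an AE only if the investigator considers it related to study intervention. It nevertheless requires an entry on the AE page of the eCRF for "all pregnancies with an estimated conception date during the period defined in Section 8.3.1", covering participants and female partners of male participants. Outcome follow-up is then required for the pregnancies just described.

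**The period referred to.** Section 8.3.1 starts at the first signature of prescreening consent and runs to the "28-day Safety Follow-up Visit, defined as 28 days (± 5 days) after the last study intervention administration". It adds that "related AEs should be documented until the last Safety Follow-up Visit", which Table 3 places at "12 Weeks (± 2 weeks) after Last Treatment". Related SAEs are reportable with no time limit.

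**Notification.** The next sentence of 8.3.5 requires expedited notification of any pregnancy on the Pregnancy Report Form and states no conception window. The section's last paragraph requires prompt notification if a participant becomes pregnant or impregnates while on study, and says that such a pregnancy is to be followed in the way already described. Section 8.3.5 does not define what counts as being on study.

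**Contraception.** Section 5.1, item 5, sets the period for men as "during the intervention period and for at least 4 months after the last dose of study intervention", and the same post-dose period for women of childbearing potential. Section 6.8.1.2 calls embryo-fetal toxicity a known class risk and gives as mitigation that pregnant participants are excluded and that "all participants of childbearing/conceiving potential must use highly effective contraception".

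**Testing.** In Table 3 the only pregnancy test after treatment is at the 28-day visit.

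**The concern.** The protocol asks participants to avoid conception for 4 months after the last dose because of a named embryo-fetal risk, yet its one explicit conception window for data entry closes earlier. Take a participant or partner who conceives 100 days after the last dose. That conception is inside the contraception period but outside the recording sentence on every reading of 8.3.1. Whether it is notified and followed depends on which other sentence of 8.3.5 the site applies.

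At stake is a complete and consistent record of exposed pregnancies and their outcomes, normal ones included, in both arms and in partners. If sites read the section differently, identical cases will be handled differently, and the eCRF will not show how many such pregnancies occurred.

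**Working it through.** The plan gives no figure of its own here, so there is nothing to reproduce. The check is date arithmetic, counted from the last dose.

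**Inputs**
- Contraception period: at least 4 months (Protocol 5.1).
- Conversion: 1 month = 30.4375 days (SAP Section 9), so 4 × 30.4375 = 121.75 days.
- End of the period for all AEs: 28 days, latest visit edge 28 + 5 = 33 days (Protocol 8.3.1).
- End of the period for related AEs: 12 × 7 = 84 days, latest visit edge 84 + 14 = 98 days (Protocol 8.3.1, Table 3).

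**Formula.** Shortfall = contraception period − end of recording window. Share = shortfall ÷ 121.75.

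| Reading of 8.3.1 | Window ends (day) | Shortfall (days) | Share |
|---|---|---|---|
| 28-day visit | 28 | 121.75 − 28 = 93.75 | 77% |
| 28-day visit, latest edge | 33 | 121.75 − 33 = 88.75 | 73% |
| 12-week visit | 84 | 121.75 − 84 = 37.75 | 31% |
| 12-week visit, latest edge | 98 | 121.75 − 98 = 23.75 | 20% |

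Visits at the early edges (days 23 and 70) lengthen the shortfalls to 98.75 and 51.75 days.

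**Sensitivity to the meaning of 4 months.** Read as 16 weeks (112 days), the four shortfalls are 84, 79, 28 and 14 days. Read as 120 days, they are 92, 87, 36 and 22. The recording window is the shorter of the two in every case.

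**Which end point applies?** Section 8.3.5 does not say. The 12-week extension is for related AEs, whereas most pregnancies recorded under 8.3.5 would not be AEs at all by its first sentence, so the 12-week reading is not secure. Section 8.2 adds a further end for the AE reporting period: the last Safety Follow-up Visit or the start of any anticancer therapy, whichever is earlier.

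**The three duties in 8.3.5 side by side**
- eCRF entry: conception within the 8.3.1 period.
- Pregnancy Report Form: any pregnancy, no window stated. The sentence directly follows the windowed one, so a site could take it as limited in the same way.
- Outcome follow-up: first for the pregnancies already described, later also for pregnancies while on study.

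**Do existing contacts reach the end of the 4 months?** Survival contacts are every 12 weeks after the last dose (Protocol 4.1). The one after the 12-week safety contact falls at about 24 × 7 = 168 days, which is 168 − 121.75 = 46.25 days after the contraception period ends.

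**The case against.** A reader might infer that pregnancies conceived after the 8.3.1 period get no Pregnancy Report Form and no outcome follow-up, so that embryo-fetal toxicity cannot be assessed over the 4 months. The documents do not support that.

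- Section 8.3.5 requires notification of any pregnancy, and its last paragraph extends follow-up to pregnancies while on study.
- Day 100 can reasonably count as on study. Protocol 4.1 includes survival follow-up of up to 5 years, 4.4 defines completion as finishing all study parts, and SAP 10.1 counts participants who are off treatment but still in the study for follow-up.
- A related SAE is reportable whenever it occurs (8.3.1), and Appendix 6 lists congenital anomaly as a seriousness criterion, so an anomaly judged related has an open-ended route.
- The protocol does not call the 4-month contraception period a risk window.

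All of this stands, and it means that the shortfalls above measure the eCRF recording sentence only. They are not days on which a pregnancy would go unreported, and they give no number of affected pregnancies.

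It does not remove the inconsistency. Neither broader sentence widens the eCRF rule. The undefined on-study condition would not clearly reach a conception after study withdrawal but within 4 months of the last dose. The related-SAE route captures only abnormal outcomes judged related, so it supplies neither a count of exposed pregnancies nor their normal outcomes. After the 28-day test, detection depends on someone volunteering the information.

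**Conclusion.** The point holds as a mismatch to be reconciled across Protocol 5.1, 8.3.1 and 8.3.5. Mandatory eCRF recording stops about 94, 38 or 24 days before the contraception period ends, for the 28-day, 12-week and 14-week readings respectively, and by at least 14 days even if 4 months is taken as 16 weeks. The recording rule and the notification and follow-up rules in 8.3.5 cover different sets of pregnancies, and detection after the 28-day test is passive.

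The conclusion rests on two assumptions: that the conception window in 8.3.5 is meant literally, and that the contraception period is a sensible yardstick for it, given that 6.8.1.2 presents contraception as mitigation of the embryo-fetal risk. It does not rest on late pregnancies being lost, which the text does not establish. This is a cheap improvement to safety data collection; the efficacy analyses are unaffected.

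**What to change.** In 8.3.5, state one conception window that governs eCRF recording, Pregnancy Report Form notification and outcome follow-up alike, for participants and for partners of male participants. Start it at consent, as 8.3.1 does now. End it no earlier than the end of the post-treatment contraception period in 5.1, by reference to that section so that the two stay aligned. The start should not be moved to first dose, because that would drop the present coverage of conceptions between consent and dosing, including early pregnancies not yet detectable at the first visit.

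Add a question about pregnancy, in the participant or a partner, at the 12-week safety contact and at the next 12-weekly survival contact. Both are already scheduled and may be done by telephone.

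The cost is a short edit to 8.3.5, one extra question at two existing contacts, and possibly a few more forms. The contraception requirement and the testing schedule do not change.
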